Symptom questionnaires will be collected at an enrollment visit (V1), and participants will be randomly assigned to the EI or DI groups. For those in the EI group, the intervention will begin 0-7 days thereafter. Sessions will be administered over 10 business days. Follow-up data collections will be obtained at 2 weeks following enrollment (V2) [0-14 days after completion of the intervention for the early intervention group], and 4-7 weeks after the V2 (V3, primary outcome). Following V3, those in the DI group will be offered the opportunity to cross over to receive 4 CR intervention sessions and will continue to be followed for data collections at 0-14 days (V4) after completing their sessions, and 4-7 weeks (V5) after V4. Mean contrasts will be used to compare the changes in measures of perceived stress (PSS) from V1 to V3, the primary outcome, in the early vs. delayed intervention groups. Similar analysis will occur for secondary outcomes.

Background, Rationale, and Context:

Background:

Abnormal electroencephalographic (EEG) asymmetries have been reported in a variety of neurological, cardiovascular, and psychophysiological conditions including insomnia, attention deficit hyperactivity disorder (ADHD), anxiety, autism spectrum disorders, depression, dyslexia, post-traumatic stress disorder (PTSD), and traumatic brain injury (TBI) (Avram, Baltes, Miclea, & Miu, 2010; T. S. Hale et al., 2010; Hale et al., 2009; T.S. Hale et al., 2010; Kemp et al., 2010; Lazarev, Pontes, Mitrofanov, & deAzevedo, 2010; Marzano, Ferrara, Sforza, & De, 2008; Metzger et al., 2004; Moscovitch et al., 2011; Rabe, Beauducel, Zollner, Maercker, & Karl, 2006; Riemann et al., 2010; Spironelli, Penolazzi, & Angrilli, 2008; Stroganova et al., 2007; Thibodeau, Jorgensen, & Kim, 2006; Wolynczyk-Gmaj & Szelenberger, 2011). Many, if not all of these conditions are associated with autonomic imbalance and

psychophysiological dysfunction manifested as low heart rate variability or other abnormal measures (Beckham et al., 2003; H. Cohen et al., 2000; Katz-Leurer, Rotem, Keren, & Meyer, 2010; Spiegelhalder et al., 2011; Tobaldini et al., 2013).

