Autonomic regulation of the cardiovascular system can be evaluated by measuring heart rate variability (HRV) or baroreflex sensitivity (BRS). HRV can indicate the physiological capacity to produce dynamically varied responses to the changing needs of an environment. Prospective studies show that decreased HRV is a risk factor for incident cardiovascular disease (Tsuji et al., 1996) and all-cause mortality (Dekker et al., 1997). In addition, depressed HRV is often reported across behavioral disorders (Beauchaine & Thayer, 2015), including military personnel and veterans with diagnosed PTSD (E. A. Lee et al., 2013; Minassian et al., 2014; J. Park et al., 2017; J. E. Park et al., 2017; Shah et al., 2013), and as a predeployment predictor of new post-deployment PTSD diagnoses or symptom severity (Minassian et al., 2015; Pyne et al., 2016). In adults, low HRV is also a risk factor for adverse cardiovascular outcomes (Kleiger, Miller, Bigger, & Moss, 1987; Tsuji et al., 1996), new onset of diabetes (Carnethon, Golden, Folsom, Haskell, & Liao, 2003), progression of chronic kidney disease (Chandra et al., 2012), and allcause mortality (Dekker et al., 1997). Due to the pervasiveness of diminished HRV in behavioral health disorders, it has also been suggested as a trans-diagnostic biomarker for psychopathology (Beauchaine & Thayer, 2015). As a measure that can be obtained easily and noninvasively, HRV warrants consideration as a target for observation and intervention on a public health basis (Marsac, 2013). HRV may also inform and support the development and dissemination of advanced practices which are beneficial for physical and mental health, or adaptive neurovisceral integration (Thayer, Hansen, Saus-Rose, & Johnsen, 2009).

A wide variety of behavioral, physical exercise, and pharmacological therapies have been shown to increase HRV (Nolan, Jong, Barry-Bianchi, Tanaka, & Floras, 2008). Especially for interventions that entail relatively non-specific features, the effects likely depend on the capacity to influence both central and peripheral nervous system pathways. An important question is whether focused engagement of critical central structures, especially those known to have specific roles for autonomic management, may be a way to produce more efficient or impactful effects on HRV.

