The bihemispheric model for autonomic management of traumatic stress (Lee SW., 2014) begins with recognition that the right and left hemispheres are primarily responsible for cortical management of the sympathetic and parasympathetic divisions, respectively. The BHAM suggests that temporal lobe electrical asymmetry may be an indication of traumatic stress exposure, associated with health effects including reduced HRV. It also suggests that interventions to reduce asymmetrical activity may be a way to de-rigidify what have become stuck stress response patterns to facilitate a state of enhanced autonomic flexibility and dynamic range, including increased HRV. Closed-loop therapies with real time monitoring for modulation of biological function offer a precision-guided, patient-centric strategy for brain-based therapies (Bellesi, Riedner, Garcia-Molina, Cirelli, & Tononi, 2014). Healthcare workers experience constant stress, exacerbated during the COVID-19 pandemic, work long hours, and are more vulnerable to developing rigidified stress responses. This study is important because it offers a nondrug, noninvasive alternative to medications to help healthcare workers mitigate, and manage stress and develop resilience.

HIRREM:

High-resolution, relational, resonance-based, electroencephalic mirroring (HIRREM®), developed by Brain State Technologies (BST), LLC, Scottsdale, AZ, is a commercially available, noninvasive, closed-loop, allostatic, acoustic stimulation neurotechnology to facilitate client-unique relaxation and autocalibration of cortical neural oscillations by echoing auditory tones in near real time (Gerdes, Gerdes, Lee, & Tegeler, 2013). HIRREM is intended to support more adaptive forms of symmetry at the temporal lobes and other cortical regions. HIRREM is aligned with the BHAM as well as the broader physiological paradigm of allostasis (stability through change), which recognizes the brain as the organ of the central command (Sterling, 2012). As a closed-loop neurotechnology (i.e., an intervention whose inputs are objectively measured real-time neurological data), HIRREM does not depend on conscious, cognitive activity, volitional self-regulation, or behavioral monitoring.

Relevant Pilot Data:

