Continuous recording (10 minutes) of blood pressure and heart rate also allowed for analysis of autonomic cardiovascular regulation, including multiple measures of HRV and BRS. This physiological data was obtained at all study visits. Analysis also demonstrated significant improvement in multiple

objective measures of autonomic cardiovascular regulation including increased BRS (HF α , and Sequence ALL) and HRV (SDNN, and rMSSD), associated with this short term use of in-office HIRREM, compared to the placebo intervention of random audible tones not linked to brainwaves (Figure 2). The benefit was seen at all follow up data collections, and was durable through the final follow up visit at 4 months post-intervention (Shaltout, Tegeler, Lee, & Tegeler, 2017). There was no significant improvement in autonomic function observed in the placebo group at any time point. It is not clear whether these results reflect a cause, an effect, or both, relative to the observed improvement of insomnia symptoms.

Figure 1:

New Developments:

In spite of the many benefits demonstrated in the above-mentioned studies, and highlighted by the placebo-controlled trial for insomnia, the in-office HIRREM approach used for research since 2011 remains very operator dependent. This, and the time required for sessions (typically 10-20 sessions of 90-120 minutes each), limit the scalability of the intervention. To reduce the length of sessions, and reduce operator dependence, while increasing scalability, an updated version of hardware, and software, with fewer sessions has been developed by BST, to be used with more standardized protocols and fewer sessions. The upgraded platform for medical research using this technology has been rebranded as Cereset Research[™] (CR). Cereset is short for "cerebral reset." Cereset is currently offered commercially as a technique for relaxation, well-being, and stress management. As a low risk general wellness device, Cereset is exempt from FDA regulation (personal communication, Brain State Technologies/Cereset)

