*** = P < 0.001								

 Table 1. Preliminary Data: Cereset Outcomes from Exploratory Open-label Study

Version 1.1 08.02.2022 Note: The mean (SD) duration from last session to V2 was 3.9 (6.0) days, from last session to V3 was 42.7 (8.6) days, last session to V4 was 83.4 (12.4) days for the table above.

Cohorts within this exploratory study are published for pain and caregivers. (C. Tegeler et al., 2021a, 2021b)

This pilot study will evaluate the effects of using this more standardized, approach, and fewer sessions with CR, in participants with self-reported symptoms of stress.

Importance:

This randomized, waitlist-controlled study will evaluate the effects of the use of CR intervention in healthcare workers with symptoms of stress during the period of COVID-19. Healthcare workers of all types have been impacted personally, professionally, and financially by the pandemic, resulting in higher levels of stress and anxiety. Additional, brief, noninvasive, non-drug strategies are needed to help mitigate the effects of the acute trauma associated with the pandemic. The primary outcome will be change in Perceived Stress Scale (PSS) a measurement of how different situations affect feelings and perceived stress, in the early intervention group compared to delayed intervention control. Data will also be collected on a variety of additional relevant symptoms including insomnia, anxiety and autonomic cardiovascular regulation, for which benefits have been shown in prior studies using HIRREM. Data collected will assess the effects of a low dose CR approach (only 4 sessions) to help participants begin to mitigate stress. A successful outcome of reduced stress would suggest benefit for this more scalable, generalizable approach to the use of the CR technology. The effect of this minimalist approach on autonomic function and other self-reported symptoms will also be explored. This information will be useful for planning larger randomized trials in more homogeneous cohorts and evaluating the appropriateness of direct clinical implementation of the intervention. The proposed study might also help to identify characteristics of individuals who may experience differential effects/benefits from this low dose application of CR.

Healthcare Worker Burden:

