Although similar in appearance to other methods such as neurofeedback, CR is distinctly different. CR uses an algorithm-based approach to allow the brain to observe, and resonate with itself. This non-judgmental, closed-loop paradigm supports the brain to auto-calibrate, self-adjust, or relax, typically resulting in shifts toward improved balance and reduced hyperarousal. There is no learner in the loop, no operant conditioning, no need to try to train one's brain to do anything. There is also no attempt to force the brain towards a standardized or ideal pattern of frequencies and amplitudes.

As with HIRREM, the exact mechanism of the effect with CR remains to be fully understood, but may involve resonance between the echoed tones and oscillating brain networks, which can be thought of as being much like a musical instrument tuning itself. A key aspect of observed beneficial effects may also be related to the observed improvement in downstream autonomic function, as evidenced by increased (improved) HRV and BRS, apparently associated with increased dynamic range and flexibility of autonomic responses managed by the brain.

Outcome Measures:

A series of measures will be collected at data collection visits (Appendix A; schedule of activities).

Primary Outcome Measure:

The Perceived Stress Scale (PSS) is a ten-item psychological instrument for measuring the perception of stress. It is a measure of the degree to which situations in one's life are appraised as stressful. Items were designed to tap how unpredictable, uncontrollable, and overloaded respondents find their lives. The scale, with answers rated from 0-4, also includes a number of direct queries about current levels of experienced stress (S. Cohen, Kamarck, & Mermelstein, 1983).

Secondary Outcome Measures:

Insomnia:

The severity of insomnia symptoms is measured using two self-report symptom inventories with each data collection visit. This includes the Insomnia Severity Index (ISI). The ISI is a 7-question measure, with responses from 0-4 for each question, yielding scores ranging from 0-28(Bastien, Vallieres, & Morin, 2001; Morin, Belleville, Belanger, & Ivers, 2011).

Anxiety:

The Generalized Anxiety Disorder-7 (GAD-7) is a seven-item screening tool for anxiety that is widely used in primary care. GAD-7 is a brief, reliable and valid measure of assessing generalized anxiety disorder (Spitzer, Kroenke, Williams, & Lowe, 2006).

Exploratory Measures:

Depression:

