Heart Rate (HR), and Heart Rate Variability (HRV):

Continuous heart rate will be recorded while the participant is breathing normally in seated position for 10 minutes using Faros 180 heart rate monitor (Bittium Corporation, Oulu, Finland). Beat to beat intervals (RRI) files will be generated at 1000 Hz via the data acquisition software. The files will be analyzed with Nevrokard HRV software (by Nevrokard Kiauta, d.o.o., Izola, Slovenia). The recordings will be visually inspected to ensure data quality (dropped beats or gross motion artifacts are excluded) and the first 5 minutes of usable tracings will be analyzed. Measures of heart rate variability (HRV) in the frequency domain will be derived and these measures will be integrated over specified frequency ranges (LF: 0.04-0.15 Hz; HF: 0.15-0.4 Hz). Power of RRI spectra in LF, HF range (LF_{RRI} and HF_{RRI}) and total power (TP) will be calculated in normalized units and the ratio of LF/HF will be used as a measure of sympathovagal balance. ("Heart rate variability: standards of measurement, physiological interpretation and clinical use. Task Force of the European Society of Cardiology and the North American Society of Pacing and Electrophysiology," 1996). Data are saved to Excel spreadsheets for further statistical analysis by study team members.

Exploration for Unexpected Barriers, Challenges, or Detrimental Factors:

A REDCap element will be added to data collection at V3 and V5, the final official data collection visit, seeking input regarding any challenges or barriers faced during the study related to factors such as availability of session dates or times, restrictive guidelines for when sessions need to occur, tasks performed during data collections, comfort of the session chair/equipment, difficulty sitting still, office location and accessibility trouble, competing other therapeutic modalities, length of the research study, or any other issues.

Analytical Plan:

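### The planned HRV measures are all relative, so with spectral-power denominators they cannot show whether overall HRV rose

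*Combined protocol and SAP*

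**What the plan says.** The HRV section of the protocol derives frequency-domain measures from the first 5 usable minutes of a 10-minute seated recording. The LF band is 0.04-0.15 Hz and the HF band 0.15-0.4 Hz. Of LF, HF and overall power it says that "total power (TP) will be calculated in normalized units and the ratio of LF/HF will be used" to represent sympathovagal balance. It gives no frequency range for total power and no denominator for the normalization. SDNN, rMSSD and power in ms² do not appear among this trial's measures. The Abstract, Objectives, Schedule of Activities and Analytical Plan refer to HRV or its recording in general terms, or cover exploratory outcomes collectively, and add no HRV measure.

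The rationale is written largely in terms of how much HRV there is:

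- Background describes "psychophysiological dysfunction manifested as low heart rate variability or other abnormal measures" and says that "depressed HRV is often reported across behavioral disorders". The bihemispheric model there aims at "enhanced autonomic flexibility and dynamic range, including increased HRV".
- CR Sessions links benefit to "increased (improved) HRV and BRS, apparently associated with increased dynamic range and flexibility of autonomic responses".
- Relevant Pilot Data reports improvement in the earlier placebo-controlled trial in "HRV (SDNN, and rMSSD), associated with this short term use of in-office HIRREM".
- Importance lists among the data to be collected "autonomic cardiovascular regulation, for which benefits have been shown in prior studies using HIRREM".

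**The concern.** A normalized band power is a share. If every measure in the set is a share or a ratio of shares, the set can show a shift between bands but not whether variability went up or down. Normalized total power looks odd for the same reason. Divided by itself it is a constant; divided by part of itself it reports only the share left out of the denominator.

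The stake is modest but real. The trial is open label with a wait-list control, and its primary and secondary outcomes are self-report scales. Heart rate and HRV are the only physiological outcomes listed in the Abstract, so they are the ones least exposed to expectation. As specified, an intervention that raised HRV proportionally across all bands would be reported as having no HRV effect. The result also could not be set beside the SDNN and rMSSD gains of the earlier trial.

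**Working it through.** The protocol gives no HRV values, so there is no figure to reproduce. The powers below are assumptions chosen to show the algebra; they do not estimate a likely loss.

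**Inputs (assumed).** LF = 800 and HF = 600 ms². O is power outside both bands, O = V + A, with V below 0.04 Hz and A above 0.4 Hz. (V, A) = (0, 0), (200, 100) or (400, 200), so O = 0, 300 or 600. TP = LF + HF + O.

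**Formula.** Normalized power = 100 × power / D. Three denominators are tried: D = LF + HF, D = TP, and D = TP − V.

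**1. Proportional change.** Multiply every power by k. Numerator and D both gain the factor k, which cancels; it also cancels in LF/HF. At O = 300, for k = 0.5, 1, 2 and 3 alike:

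| D | LFnu | HFnu | TPnu | LF/HF |
|---|---|---|---|---|
| LF+HF = 1400k | 57.1 | 42.9 | 121.4 | 1.33 |
| TP = 1700k | 47.1 | 35.3 | 100 | 1.33 |
| TP−V = 1500k | 53.3 | 40.0 | 113.3 | 1.33 |

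Over the same range TP runs 850, 1700, 3400, 5100 ms². Doubling raises ln TP by ln 2 = 0.69, and SDNN and rMSSD by √2 − 1 = 41%. The invariance also holds at O = 0 and O = 600.

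**2. A rise and a fall that look the same.** Compare HF doubled, giving (LF, 2HF, O), with LF and O halved, giving (LF/2, HF, O/2). The first is exactly twice the second, so every ratio agrees under all three denominators:

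| O | Baseline TP | TP, HF doubled | TP, LF and O halved | LFnu, HFnu, TPnu in both (D = LF+HF) |
|---|---|---|---|---|
| 0 | 1400 | 2000 (+43%) | 1000 (−29%) | 40, 60, 100 |
| 300 | 1700 | 2300 (+35%) | 1150 (−32%) | 40, 60, 115 |
| 600 | 2000 | 2600 (+30%) | 1300 (−35%) | 40, 60, 130 |

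LF/HF is 0.67 in every case. At O = 300, taking SDNN as √TP (TP covering the full range), SDNN goes from 41.2 ms to 48.0 or to 33.9 ms.

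**3. What normalized TP measures.** With D = LF + HF, TPnu = 100 × [1 + O/(LF + HF)]. With D = TP it is always 100. With D = TP − V it is 100 × [1 + V/(LF + HF + A)]. It is a constant or an out-of-band share, and it can move against actual power. At O = 300 with D = LF + HF:

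- HF doubled: TP rises to 2300, and TPnu falls from 121.4 to 115.
- LF alone halved: TP falls to 1300, and TPnu rises to 130.

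This pair is separated, so the set does not always confuse a rise with a fall, but TPnu points the wrong way.

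**4. A denominator that escapes.** With D = mean RR interval squared (800 ms assumed, 800² = 640,000), doubling moves normalized TP from 1700/640,000 = 0.27% to 3400/640,000 = 0.53%. LF, HF and TP would then respond, and the problem would not apply to them. The protocol does not name such a denominator.

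**Check with other inputs.** VLF 400, LF 600, HF 500 ms², with D = LF + HF: TP goes from 1500 to 3000 when power doubles, while LFnu 54.55, HFnu 45.45, TPnu 136.36 and LF/HF 1.20 stay fixed. A synthetic 5-minute RR series behaved the same way: SDNN went from 34.2 to 48.3 ms on doubling power, with all four planned measures unchanged.

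**The case against.** The best reply is that this is a units slip. Total power in normalized units carries so little information that the author may have meant absolute units, in which case the set already holds one overall measure. That may be so, and the fix is then one line. As written, however, the unit rule covers total power, and an analyst following it would export no overall measure.

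Second, the denominator is unseen. The section cites a published standard and names the software, either of which may define it. That limits certainty about the consequence, and step 4 shows a normalization that avoids it. It does not remove the need for the protocol to say which one applies.

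Third, the rationale is not solely about amount. Background also mentions autonomic imbalance and other abnormal measures, which LF/HF serves. The Objectives state no direction for HRV, and the passages naming increased HRV are model and mechanism text. The section also does not forbid time-domain measures; it omits them. All of this stands, and it means that no planned hypothesis test is contradicted. The protocol nevertheless names increased HRV as the benefit in two places and lists nothing that would measure it.

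Finally, HRV is exploratory in a pilot trial, and the RR-interval files allow absolute measures to be calculated later. This is right and keeps the point modest. The remaining cost is that indices chosen after the data are seen are post hoc, while Importance says the information is meant to help plan larger trials.

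**Conclusion.** The concern holds. With D equal to LF + HF, TP, or TP less power below 0.04 Hz, the four planned measures are fixed by the shares of power alone. A proportional change of any size is invisible, and some non-proportional rises and falls (+35% against −32% in total power at O = 300) give identical results. The set suits the sympathovagal-balance part of the rationale but not the increased HRV named in Background and CR Sessions.

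The algebra is certain; the consequence depends on the denominator being spectral power from the same recording and on normalized total power being meant as written. The powers are illustrative, so no likely loss is claimed. Heart rate and the primary and secondary outcomes are unaffected. This is a worthwhile, inexpensive improvement and not a threat to the trial's main result.

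**What to change.** In the HRV section:

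- State total power, LF and HF in ms², log-transformed, and give the frequency range for total power.
- Add SDNN and rMSSD from the same 5-minute RR-interval segments.
- Keep one relative measure, LF/HF or LFnu, with its denominator stated.
- Drop normalized total power and the redundant normalized bands (with D = LF + HF, LFnu and HFnu sum to 100 and LF/HF is their ratio).
- Compare the arms on V1 to V3 change by the contrast already in the Analytical Plan, labelled exploratory.

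No new recordings are needed. The cost is revised wording and a few more exported variables: the set goes from four (LFnu, HFnu, TPnu, LF/HF) to six (ln LF, ln HF, ln TP, SDNN, rMSSD, one relative measure), which adds two exploratory comparisons. If the sponsor wants the smallest change, stating total power in absolute units with its frequency range restores one overall measure.

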Within the healthcare field, studies have shown that healthcare workers have a higher prevalence of anxiety, depression, somatization, and insomnia to nonmedical health workers (Liang, Chen, Zheng, & Liu, 2020; McAlonan et al., 2007; K. Zhang, Zhou, Liu, & Hashimoto, 2020; Y. Zhang & Ma, 2020). Without new interventions or solutions to mitigate increased arousal, healthcare workers are at a higher risk of developing long-lasting health impacts of stress related to COVID-19. One study highlighted that more than half of healthcare professionals reported depressive symptoms, 44.7% reported anxiety, and 36.1% sleep disturbance (S. Liu et al., 2020). Frontline workers also show more severe degrees of mental health symptoms than other healthcare workers (Lai et al., 2020).

Sleep and social support are hypothesized to help mitigate the effects of stress on the body and decrease PTSS symptoms, specifically levels of anxiety, stress, and self-efficacy (N. Liu et al., 2020; Xiao, Zhang, Kong, Li, & Yang, 2020)).

This study will focus on a heterogeneous group of healthcare workers including physicians, nurses, support staff (PA, NP, respiratory therapists, diagnostic personnel, etc.), mental health professionals, administration, and medical center staff.

Objectives:

The primary objective of this study is to evaluate the effect of CR to improve the Perceived Stress Scale (PSS) in healthcare workers with symptoms of stress, compared to waitlist control, at 4-6 weeks post intervention.

The secondary objective is to evaluate the effect of CR on self-reported symptom inventories of insomnia and anxiety. We will also evaluate exploratory measures for mood, post-traumatic stress, quality of life, social support, cognitive function, and autonomic cardiovascular regulation (heart rate variability, HRV).

Methods and Measures:

Design:

This will be a single site, open label, randomized, wait-list controlled, pilot clinical trial.

Setting:

Study visits and sessions will be conducted in [name].

Subjects Selection Criteria

Participants/Subjects:

Healthcare workers aged 18 and older with symptoms of stress, who also meet the inclusion criteria outlined below, and are interested in receiving CR, will be offered enrollment. The participant must be able to provide informed consent.

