Confidentiality will be protected by collecting only information needed to assess study outcomes, minimizing to the fullest extent possible the collection of any information that could directly identify subjects, and maintaining all study information in a secure manner. Per institutional policy, all research study participants will be assigned a hospital MRN number, if none already exists. To help ensure subject privacy and confidentiality, only a unique study identifier number, and first name will appear on the data collection form. Any other collected patient identifying information corresponding to the unique study identifier will be maintained on a separate master log. The master log will be kept secure, on a separate, limited access user group on a shared network drive, with access limited to designated study personnel. Following data collection, subject identifying information will be destroyed at the earliest opportunity, consistent with data validation and study design, producing an anonymous analytical data set. Data access will be limited to study staff. Data and records will be kept locked and secured, with any computer data password protected. No reference to any individual participant will appear in reports, presentations, or publications that may arise from the study.

Brain State Technologies, LLC (BST) may assist with brain pattern review and analysis. To accomplish this, BST is provided with the first 8 characters from the randomly generated, 36-character identifier that the HIRREM software generates for each participant's brain frequency and amplitude data, along with the participant's age and gender, which are believed important for understanding brain patterns. No other participant-specific information is provided.

Safety:

Based on experience reported by Brain State Technologies/Cereset, garnered from provision of case management support, feedback from their clients (now reported to be about 130,000), and feedback

from the HIRREM provider community, as well as results from IRB-approved studies at WFSM (now over 600 participants to receive HIRREM), we are not aware of any serious adverse events resulting from HIRREM sessions.

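### HRV artefact review is done by eye in an open-label trial, and the plan does not say that the reader is masked to arm or visit

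*Combined protocol and SAP*

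**What the plan says.** The Design section states: "This will be a single site, open label, randomized, wait-list controlled, pilot clinical trial".

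The section on heart rate and HRV sets out the measurement: "Continuous heart rate will be recorded while the participant is breathing normally in seated position for 10 minutes". Beat-to-beat interval (RRI) files are then generated and analysed in HRV software. On data quality it says "The recordings will be visually inspected to ensure data quality", names missed beats and gross movement artefact as the exclusions, and adds that "the first 5 minutes of usable tracings will be analyzed". LF, HF, total power and LF/HF follow from that segment. The section closes with "Data are saved to Excel spreadsheets for further statistical analysis by study team members".

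The Schedule of Activities places an HRV recording at V1, V2 and V3 in both arms, and at V4 and V5 in the delayed arm after crossover. The Analytical Plan applies the V1-to-V3 mean contrast between arms to the exploratory outcomes as well as to PSS. The Abstract and Objectives class HRV as exploratory.

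Under Confidentiality and Privacy, "Data access will be limited to study staff". No section describes a masked HRV reader, a masked HRV analyst, or recoding of the HRV files.

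**The concern.** All the other listed outcomes are questionnaires or reported counts, supplied by participants who know whether they have had the sessions. HR and HRV come from a device, so the participant's own rating does not enter the value. A human judgement does enter when someone decides which stretches of tracing are artefact.

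That decision affects the result. Excluding a noisy stretch, or accepting it, moves the start or the content of the five-minute segment, and the spectral measures are computed from that segment. If the reader knows the arm and the visit, borderline calls can drift in one direction without any intent. The effect would then appear as a difference between arms in HRV change. At stake is how far an exploratory HRV finding can be trusted, not the primary conclusion.

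**Working it through.** The plan gives no figure to reproduce, so the check sets the relevant statements side by side. An illustration on an assumed scale follows.

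**1. Is there judgement in the reading step?** Yes. Inspection is visual and the exclusions are named by type, but no threshold is given, such as a percentage of beats or a deviation from neighbouring intervals.

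**2. How far is that judgement constrained?** The segment is the first five usable minutes, not any five minutes. The recording lasts 10 minutes, so at most 10 − 5 = 5 minutes can be passed over before too little is left. Reaching that limit would mean rejecting half the tracing as artefact. The room for discretion is real but bounded, and it lies in the meaning of usable.

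**3. Which recordings feed the between-arm contrast?** The contrast is change from V1 to V3, and V1, V2 and V3 are recorded in both arms. V4 and V5 exist only in the delayed arm and fall outside it.

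**4. What must the reader know for bias to arise?** Knowing the visit alone would tend to shift both arms alike and largely cancel in a difference of changes. Bias between arms needs knowledge, or a good guess, of the arm. The trial is open label and access to data is confined to study staff. The document neither names the reader nor states that this person lacks that knowledge.

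**5. Illustration only.** Inputs: 138 target completers (Sample Size section); 69 per arm, assuming 1:1 allocation because no ratio is stated; two-sided 5% test; no true effect; and an assumed bias b between arms, in SD units of the HRV change. The standard error in SD units is √(2/69) = 0.170. The false-positive rate is P(|Z + b/0.170| > 1.96).

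| Assumed b (SD) | b / 0.170 | False-positive rate |
|---|---|---|
| 0 (masked reading) | 0 | 5.0% |
| 0.05 | 0.29 | 6.0% |
| 0.10 | 0.59 | 9.0% |
| 0.20 | 1.17 | 21.7% |
| 0.30 | 1.76 | 42.2% |

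The values of b are not taken from the documents and are not estimates for this trial. The table shows only that a small systematic drift would matter at this sample size, and that masking the reading step costs no participants.

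**The case against.** The strongest reply is that the plan already narrows the reader's freedom and that the document is silent on masking, which is not the same as ruling it out. Both parts stand. The rule fixes the earliest usable five minutes and names what is excluded, so a reader who infers that staff pick the minutes they like goes beyond the text. It is also possible that masked reading is the group's practice and was not written down, and part of the text around the Safety section was not available to this review.

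Three further inferences are tempting and are not supported:

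- **That the reader knows the participants or sees their names.** The confidentiality section says "only a unique study identifier number, and first name will appear on the data collection form", but that concerns the form. Nothing says that the RRI files carry names, or that the person inspecting them meets participants. The study identifier and the separate master log are privacy measures, so they show neither masking nor its absence.
- **That the delayed arm's extra visits reveal the arm.** Those recordings lie outside the V1-to-V3 contrast, and a V1, V2 or V3 tracing does not by itself show the arm.
- **That HRV is this trial's objective check on PSS.** No section gives it that role. The Sample Size section rests the case for clinical implementation on a three-point PSS difference.

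It is also fair to say that no direction of bias has been shown, since the plan does not state which direction of LF/HF would favour the intervention. What survives is that visual judgement without a numeric criterion, in an open-label trial, has no stated masking.

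**Conclusion.** The point holds as a modest one: masking of HRV artefact review is not stated, and the reading step is therefore open to observer bias. The size cannot be derived from the documents. The PSS result and the secondary questionnaire outcomes do not depend on it.

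The conclusion assumes that the reader has, or could obtain, knowledge of arm, which the open-label design permits but the document does not confirm. If files are already coded before inspection, a sentence saying so closes the matter.

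A reader might infer that masked reading would make HRV free of expectation. It would not. Participants know their arm while they sit for the recording, and staff may know it too. Resting autonomic state at that moment may respond to this knowledge, and recoding files afterwards leaves any such effect in place.

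**What to change.** In the section on heart rate and HRV, state that:

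1. before visual inspection, each RRI file is renamed with a random code, and name, arm, visit and date are stripped from the file name and header;
2. artefact exclusion, segment selection and spectral output are completed and locked under that code;
3. codes are linked to participant, visit and arm only after the lock.

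The same reader and software can be used. The cost is a renaming script, a key file that the reader does not hold (the study coordinator could keep it), and a slight delay because files are processed in coded batches. No extra visit, participant or procedure is needed. The study already uses coded files elsewhere: the confidentiality section has brain-pattern data going to the manufacturer under a truncated random identifier.
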